7.2. Ocular Toxicity

Maytansinoids are known to cause ocular toxicity when used as the payload in ADCs. IMGC936-related ophthalmic findings were observed in repeat-dose nonclinical studies. These findings included reversible ocular events, eg, discharge, conjunctival swelling, congestion and/or cloudiness, pannus, cellular or keratic precipitates, and corneal pigmentation in one or both eyes and microscopic changes of minimal to moderate single cell necrosis and minimal to mild increased mitoses.

Ocular events have been observed in patients receiving IMGC936 in clinical trials. As such, participants should be monitored for symptoms with each cycle and action taken as noted below both to monitor for and manage ocular toxicity should it arise. Ocular symptoms and signs to be closely monitored are included but not limited to those defined in the IMGC936 Investigator's Brochure, Section 6.6.2.

For participants in dose escalation cohorts in Schedule A, ocular symptom assessment should occur weekly during the first 3 cycles and subsequently on Day 1 of each cycle. For participants in dose escalation cohorts in Schedule B, ocular symptom assessment should occur weekly in Cycle 1 and 2, and occur on Day 1 and Day 8 in each subsequent cycle. Participants' ocular symptoms and signs are also evaluated on Cycle 3 Day 15.

During the Dose Expansion Phase (at the RP2D), if ocular toxicity is limited (eg, does not lead to dose reductions or discontinuations in > 10% of participants) at the RP2D during escalation, ocular symptom assessment will occur on Day 1 of each cycle or more frequently if ocular symptoms or signs are observed. Phone-based ocular symptoms assessments are acceptable if no clinic visit is scheduled. If a participant develops ocular symptoms or signs of any grade (eg, blurred vision, dry eye, eye pain), the participant is required to have a complete ophthalmic examination by an ophthalmologist. If a participant develops ≥ Grade 2 ocular symptoms or signs, the study drug must be interrupted. Study drug may resume if ocular symptoms or signs improve to Grade 1 or baseline within 14 days (see Table 7 for details). Subsequent ophthalmic examinations will be scheduled to occur in every other cycle going forward, from the time that the AE was initially reported until resolution to Grade 1 or less, stabilization, or return to baseline, even after study drug discontinuation, if needed.

Note: To monitor for asymptomatic ocular effects, all participants will be required to have an ophthalmic examination at screening, the end of Cycle 2, and then approximately every 3 cycles (ie, Cycle 5, 8, 11, etc.) regardless of whether they reported any ocular symptoms or signs. Participants with Grade 2 or greater ocular AE which have not resolved to Grade 1 or baseline must have an ophthalmic examination at EOTV.

All participants should use a prophylactic regimen of lubricating artificial tears to mitigate ocular symptoms and signs. In certain circumstances, additional prophylactic eye drops may also be given, including the outlined options below.

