4.1.1. Dose Escalation

The primary objective of the Dose Escalation Phase of the study is to characterize safety and tolerability of IMGC936 to define the single-agent MTD and select a RP2D. If no MTD is defined after escalation to the maximum protocol-specified dose, then the highest dose level administered will be designated as the MAD.

Up to 72 evaluable participants will be enrolled in the Dose Escalation Phase of this study.

Dose escalation follows a conventional 3 + 3 design: successive cohorts of 3 to 6 participants each will be evaluated in sequential escalating doses of single-agent IMGC936 (Table 2).

Each cycle is 21 days for Schedule A. IMGC936 is administered via IV infusion on Day 1 of Cycle 1 and every subsequent 21-day cycle thereafter at the assigned dose for each cohort in Schedule A. Infusion duration will vary depending on dose and participant tolerability. Sentinel dosing will be used for the first 2 dose levels. The first administration of IMGC936 (Cycle 1) in participants at the first 2 dose levels of Schedule A dose escalation will be staggered by at least 48 hours.

Upon agreement between investigators and the sponsor, intermediate dose levels may be evaluated based on review of cumulative safety and PK data. For example, participants have been enrolled in intermediate dose cohorts at doses of 5 mg/kg and 6 mg/kg.

Table 2: IMGC936 Dose Levels: Dose Escalation

Cohort	IMGC936 Dose
Cohort 1	0.5 mg/kg
Cohort 2	1.0 mg/kg
Cohort 3	2.0 mg/kg
Cohort 4	4.0 mg/kg
Intermediate Dose	5.0 mg/kg
Intermediate Dose	6.0 mg/kg
Cohort 5	7.0 mg/kg
Cohort 6	10.0 mg/kg
Cohort 7	12.0 mg/kg

Dose escalation will follow standard 3 + 3 design until an MTD or MAD is established. To support the selection of the RP2D, upon agreement between investigators and the sponsor, any dose level not exceeding the MTD may be expanded to a maximum of 15 participants for further evaluation of safety, PK, antitumor activity, to facilitate selection of the RP2D. Intermediate dose levels, not exceeding the MTD, may also be explored.

Participants on Schedule A who are not able to complete the 21-day evaluation secondary to AEs considered unrelated to study drug or any other cause unrelated to study drug are considered unevaluable for safety and toxicity during the DLT evaluation period and may be replaced.

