4.1.3. Eye Drop Sub-Study

4.1.3.1. Sub-Study Schema

4.1.3.2. Sub-Study Design

Up to 60 participants from Cohorts A to G may voluntarily consent to join a sub-study to evaluate the effect of different prophylactic eye drops, beyond standard lubricating eye drops. Consenting participants will be assigned to cohorts of 10 to 20 participants who will receive additional eye drops as primary prophylaxis to mitigate ocular symptoms and signs. Participants in this sub-study will be monitored for the frequency and severity of ocular events and will have an ocular examination after 2 cycles of therapy regardless of whether they have ocular symptoms and signs, as required of all participants in this trial. Major differences in ocular AEs (eg, 50% reduction in participants with ≥ Grade 2 keratopathy, or 50% reduction in ocular AEs leading to dose reduction/discontinuation) will be used to determine whether different eye drop regimens provide benefit in comparison to others and to participants on trial that only receive prophylactic lubricating drops. Knowledge gained from this sub-study may be applied to the remainder of the study participants. Details of the eye drop options are described in Section 7.2.1.

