Ocular symptoms and signs assessment will be performed by the treating physician or other qualified individual. For participants reporting > Grade 1 ocular symptoms and signs, treatment will be held until the participant is evaluated by an ophthalmologist for a complete examination (Section 7.2).

Participants in the ocular sub-study will be monitored for the frequency and severity of ocular events as usual. Participants without ocular symptoms or signs should have an ophthalmic examination at the end of Cycle 2 and followed with ophthalmic examinations every three cycles until the end of treatment. Participants with ocular AEs must have ophthalmological examinations per Table 7, but will be required to have an early ocular examination after 2 cycles of therapy (instead of after 3 cycles) regardless of whether they have ocular symptoms and signs.

9.13. **Archival Tumor Tissue**

Participants must submit archival tumor tissue (FFPE block, or unstained slides) for analysis of ADAM9 expression. If a participant does not have archival material available for analysis, the participant may alternatively undergo a low-risk, medically routine procedure to obtain a tissue sample, if appropriate. The decision to biopsy will be made once participant eligibility has been determined and on the basis of tumor accessibility and participant safety. This will typically require that the tumor lesions are superficially accessible or that the lesions can be biopsied under CT or ultrasound guidance without traversing major blood vessels or other vital structures. The specimens will be analyzed retrospectively and will not be used to determine participant

eligibility. Instructions regarding processing and shipment of archival tissues and biopsy samples are detailed in the Laboratory Manual.

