- b Includes height (screening only) and weight. Weight may be obtained within 24 hours of Cycle 1 Day 1. Full physical examinations are performed at screening, Cycle 1 Day 1 (or within 24 hours before the first infusion), and EOTV. All other physical examinations are directed physical examinations based on symptoms, tumor location, and as clinically indicated. Participants in dose escalation cohorts will have weekly directed physical examination through treatment Cycle 3. Beginning on Cycle 4, physical examination is only required on Day 1 of each cycle. Participants in the dose expansion cohorts should have physical examination recorded on Day 1 of each treatment cycle.
- ^c ECOG performance status should be the primary performance measure for participant enrollment. If ECOG performance status is an inappropriate performance measurement for participant enrollment (eg, chronically nonambulatory), then Karnofsky performance status may be used. A description of the scale is in Appendix 8. ECOG assessment at C1D1 can be performed within 24 hours before the infusion.
- d On Day 1 of Cycle 1, 2 and 3, ECGs are recorded pre-infusion (within 30 minutes before) and EOI (within 30 minutes after EOI). During selected non-dosing visits (eg, screening, C1D8, and EOTV), ECGs will be recorded.
- ^e The Investigator to choose appropriate modality (eg, echocardiogram or MUGA) to assess LVEF.
- ophthalmic examinations are performed at screening by an ophthalmologist per Section 9.12. All participants will have a complete ophthalmological examination when ocular symptoms and signs develop, repeated per Table 7. Participants without ocular symptoms or signs should have an ophthalmic examination at the end of Cycle 2, followed with ophthalmic exams every 3 cycles/ 9 weeks (at the end of Cycle 5,8, etc.) in both dose escalation and expansion phases. Participants with Grade 2 or greater ocular AEs which have not resolved to Grade 1 or baseline must have an ophthalmic examination at EOTV. All other participants are recommended to have an ophthalmic examination at EOTV to document any subclinical findings.
- ^g Ocular symptom assessment at C1D1 can be performed within 24 hours before the infusion. For participants in dose escalation cohorts, ocular symptoms assessment should occur weekly during the first 3 cycles and subsequently Day 1 of each cycle. During the Dose Expansion Phase (at RP2D), if limited ocular

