The criteria for eye drop subgroups are defined as follows.

Brimonidine + lubricating eye drop group: patient who started brimonidine prior to or on C1D1 reported in concomitant medicine or cycle 1 eye drop compliance form.

Steroid + lubricating eye drop group: patient who started steroid prior to or on C1D1 reported in concomitant medicine or cycle 1 eye drop compliance form.

Lubricating only eye drop group: all other patients at 6 mg/kg who are not included in above two groups.

The following AE summary tables will be produced:

- An overall summary: present the numbers (and percentages) of patients with any TEAEs, TEAEs ≥ Grade 3, study drug related AEs, AEs leading to permanent discontinuation of study drug, TEAEs leading to death, and any death during the study treatment or within 30 days of last dose.
- All TEAEs
- TEAEs with CTCAE severity Grade  $\geq 3$
- Study drug related TEAEs (ie, TEAEs with a drug relationship of possibly related, probably related, or definitely related; TEAEs with missing drug relationships will be also included).
- Study drug related TEAEs with CTCAE severity Grade  $\geq 3$
- Serious TEAEs
- Non-Serious TEAEs (ie, TEAEs excluding SAEs)

Confidential and Proprietary ImmunoGen, Inc.

- Study drug related SAEs
- TEAEs leading to discontinuation of study drug (ie, TEAEs with an action taken of study drug discontinued permanently)
- TEAEs leading to interruption of study drug (ie, TEAEs with an action taken of study drug with dose interrupted)
- Study drug related TEAEs leading to discontinuation of study drug
- Study drug related TEAEs leading to interruption of study drug
- TEAEs leading to death (ie, TEAEs with CTCAE Grade 5)
- Deaths on study treatment or within 30 days of the last dose. This table includes all deaths during study treatment or within 30 days of the last dose, regardless of cause of death.
- Ocular TEAE resolution (blurred vision and keratopathy)
- Time to onset of first ocular TEAE (blurred and keratopathy)

Time to resolution of ocular TEAE (blurred vision and keratopathy)The following listings will be produced:

- All pre-treatment AEs
- All TEAEs, sorted chronologically within patient. This listing includes SOC, PT, onset and end dates, and other relevant information.
- Serious TEAEs, sorted chronologically within patient
- TEAEs leading to discontinuation of study drug
- TEAEs leading to interruption of study drug
- Study drug related TEAEs
- Study drug related SAEs
- Dose-limiting toxicities (DLTs)

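### The SAP's 6 mg/kg eye-drop comparison can mix weekly and once-per-cycle symptom checks, so short-lived ocular events may look rarer with extra drops for reasons of ascertainment

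*Protocol*

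**What the plan says.** Protocol 7.2 sets two intensities of symptom checking. For Schedule A escalation, "ocular symptom assessment should occur weekly during the first 3 cycles and subsequently on Day 1 of each cycle". For expansion, a lighter schedule is conditional: "if ocular toxicity is limited (eg, does not lead to dose reductions or discontinuations in > 10% of participants) at the RP2D during escalation", then "ocular symptom assessment will occur on Day 1 of each cycle or more frequently if ocular symptoms or signs are observed". Appendix 1 repeats both and adds "Ocular symptom assessment at C1D1 can be performed within 24 hours before the infusion", so the first check can precede any exposure.

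The dose level spans both phases. Protocol 4.1.1 records that "participants have been enrolled in intermediate dose cohorts at doses of 5 mg/kg and 6 mg/kg", and 6 mg/kg is listed only among the Schedule A levels. SAP 7 takes 6 mg/kg as the RP2D and plans a combined column for it, with no split by phase. SAP 7.2 then divides the 6 mg/kg patients into brimonidine, steroid and a remainder: "Lubricating only eye drop group: all other patients at 6 mg/kg who are not included in above two groups". SAP 7.11 sends findings from the ocular assessments into the TEAE tables.

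The assigned prophylaxis groups have a narrower source. Protocol 4.1.3.2 states: "Up to 60 participants from Cohorts A to G may voluntarily consent to join a sub-study". Cohorts A to G are all expansion cohorts. The same section judges benefit partly against participants on lubricating drops alone. Its examples of a major difference are a halving of participants with Grade 2 or worse keratopathy, or of ocular events that change or stop dosing.

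**The concern.** The groups can differ in how often participants are asked about ocular symptoms as well as in the drops they receive. Escalation patients without extra drops enter the reference with weekly questioning. Sub-study patients may be questioned once per 21-day cycle. A transient symptom that starts and ends between two Day 1 visits is more likely to be recorded in the first group than in the second.

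Nothing in the SAP separates this from a drug effect: the groups are not restricted to or stratified by phase, and SAP 4.6 plans no covariate adjustment. What is at stake is the reading of the eye-drop tables, which Protocol 4.1.3.2 says may guide prophylaxis for the remaining participants.

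**Working it through.** The plan gives no sample size, event rate or detection figure for this comparison, so there is no stated figure to reproduce.

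**Scheduled checks, Schedule A** (Protocol 7.2 and Appendix 1, 21-day cycles):
- Escalation, Cycles 1-3: Days 1, 8, 15, 22, 29, 36, 43, 50, 57, which is 9.
- Expansion on the lighter schedule: Days 1, 22, 43, which is 3.
- Treating Day 1 as pre-dose and counting through Cycle 4 Day 1 (Day 64), the post-dose counts are again 9 and 3. The first falls on Day 8 and Day 22 respectively.

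**Detection model.** Let an episode last *d* days, with onset uniform over the interval *I* between checks (7 or 21 days). Let *q* be the share captured anyway through self-report between visits.
- Detection: C(I) = q + (1 − q) × min(1, d/I)
- Reference with escalation share *f*: R = f × C(7) + (1 − f) × C(21)
- Apparent reduction with no true effect, extra-drop group all expansion: 1 − C(21)/R

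The documents give none of *d*, *q* or *f*, so all three are assumptions. Fourteen days serves as the main illustration because Table 7 uses it as a recovery threshold for Grade 2 events.

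**Worked case, d = 14**
- f = 1, q = 0: C(21) = 14/21 = 0.667, R = 1, reduction 33%.
- f = 1, q = 0.5: C(21) = 0.5 + 0.5 × 0.667 = 0.833, R = 1, reduction 17%.
- f = 0.5, q = 0: R = 0.5 + 0.5 × 0.667 = 0.833, reduction 1 − 0.667/0.833 = 20%.
- f = 0.5, q = 0.5: R = 0.5 + 0.5 × 0.833 = 0.917, reduction 1 − 0.833/0.917 = 9%.

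| Episode length | Reference all escalation (q = 0 / q = 0.5) | Reference half escalation (q = 0 / q = 0.5) |
|---|---|---|
| 7 days | 67% / 33% | 50% / 20% |
| 10 days | 52% / 26% | 35% / 15% |
| 14 days | 33% / 17% | 20% / 9% |
| 21 days or longer | 0% / 0% | 0% / 0% |

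**Onset.** The mean wait to the next scheduled check is 7/2 = 3.5 days against 21/2 = 10.5 days. This would shift analysed time to onset only if the onset date were taken as the detection visit. SAP 4.3.1 works from a recorded onset date, so 7 days is an upper limit.

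**The case against.** The strongest reply is that scheduled symptom checks are only one route to an ocular event.

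- Appendix 1 has AEs assessed continuously in both phases. A symptom between visits can be reported at the next one with its true onset date.
- Appendix 4 places PK draws on Days 8 and 15 of Cycles 1 and 3 and Day 15 of Cycle 2, without restricting them to escalation. Expansion participants are therefore seen in most non-dosing weeks.
- Eye examinations at screening, the end of Cycle 2 and about every three cycles after that apply to everyone (Protocol 7.2 and 9.12).
- The reference also contains expansion patients without extra drops. As an illustration, suppose Cohorts A to E fill at 6 mg/kg (5 × 39 = 195), 60 join the sub-study and 15 come from escalation. The escalation share is then 15/(195 − 60 + 15) = 10%, and 14-day episodes give 1 − 0.667/0.70 = 5% with no self-report.

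All of this stands and limits the size. It does not remove the mechanism, because weekly questioning still prompts reports that open recall may miss, and Protocol 7.2 makes any symptom a trigger for a full eye examination.

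Three stronger readings are tempting and not supported:

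- A reader might infer that the schedule alone can meet the protocol's 50% example, since the 7-day row reaches 67%. That row needs an all-escalation reference and no self-report. The example concerns Grade 2 or worse keratopathy or dose-changing events, not brief symptoms of any grade. Under Table 7 a Grade 2 event leads to a lower dose level only if recovery takes more than 14 days, where the model gives at most 33%, falling to zero at 21 days.
- A reader might extend the bias to time to resolution. Table 7 requires weekly symptom follow-up at every grade, in either phase, once an event is found.
- A reader might take the lighter schedule and the direction of bias as settled. The documents do not say the 7.2 condition was met. Section 7.2.1 lets participants outside the sub-study receive extra drops, and the SAP assigns groups from medication or compliance records, so some escalation patients may sit in the extra-drop groups.

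**Conclusion.** The point holds conditionally. If the lighter expansion schedule applies, the SAP 7.2 comparison can show fewer short-lived ocular symptom events with extra drops because of unequal checking. Recorded onset can be affected to a lesser degree. For 14-day episodes and no true effect the apparent reduction is about 17-33% with an all-escalation reference and 9-20% with half, and it is less if escalation patients are few. It is zero for episodes of 21 days or longer. These figures assume Schedule A, uniform onset, extra drops confined to expansion, and self-report between none and half.

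Keratopathy and dose-changing events are less exposed because the fixed examinations are shared. SAP 4.10 plans no hypothesis test, so the harm is a misleading descriptive table, not an inflated error rate. If the 7.2 condition was not met, the text sets no lighter schedule and the mechanism falls away. The point is worth correcting because the remedy is cheap and uses data already collected.

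**What to change.** In SAP 7.2, make the main eye-drop comparison, for ocular TEAE incidence and time to onset, among expansion-phase 6 mg/kg participants on the same assessment schedule. Show escalation 6 mg/kg participants in a separate column, and split the ocular rows of the combined 6 mg/kg summary by phase. With equal intervals C(I) is the same in both groups, so the artificial reduction is zero.

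The cost is some SAP wording, one more column and a somewhat smaller lubricating-only reference. The loss is at most the escalation 6 mg/kg cohort, which Protocol 4.1.1 caps at 15 if expanded. Participant monitoring does not change.

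Separately, Protocol 9.12 says of sub-study participants with ocular AEs that they "will be required to have an early ocular examination after 2 cycles of therapy (instead of after 3 cycles"), whereas 4.1.3.2 and 7.2 require the two-cycle examination of everyone. These passages must be reconciled.

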4.3. Expansion Phase Safety Monitoring

Safety will be evaluated continuously and in aggregate in the expansion cohorts. Safety assessments will be based on all TEAEs and abnormal laboratory values. If at any time \geq 33% of at least 3 participants who received study drug in an expansion cohort experience a study drug—related TEAE leading to discontinuation, enrollment will be paused within that cohort and may also be paused in ongoing cohorts at the discretion of the sponsor. If it is determined that the clinical investigation should be halted due to an unacceptable participant risk, the study must be terminated after appropriate consultation between the sponsor and investigators.

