4.5.1. Dose Delays

Participants who experience toxicity should have study drug held pending assessment, management, and resolution of the toxicity. If the toxicity is assessed as unrelated to study drug or does not meet DLT criteria, study drug may be restarted at the previous dose and schedule, after consultation with the medical monitor. The toxicity should have resolved prior to reinstitution of study drug per guidelines outlined in Section 7. Reinstitution of study drug shall be conducted as follows:

• Dose delays of up to 21 days are allowed for participants who experience toxicity. This may include 1 missed dose of IMGC936 on Schedule A and 2 missed doses on Schedule B. The procedures at the originally scheduled missed visit should be performed as soon as possible with study drug reinstituted as if no delay had occurred, picking up at the day where the interruption occurred per the schedule in Appendix 1 and Appendix 2. Participants who have a dose delay of > 21 days may restart study drug with discussion and approval of the sponsor.

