7.2.2. Management of Ocular Symptoms and Signs

Table 7: Management of Ocular Symptoms and Signs

Grade (CTCAE v5.0)	Management	Guidelines for Dose Modification ^a
Grade 1	Complete eye examination. Participants should have weekly symptomatic ocular assessments to monitor for worsening symptoms and signs and repeat eye examinations as needed.	Continue study drug dosing.
Grade 2	Complete eye examination. Participants should have weekly symptomatic ocular assessments and repeat eye examinations at least every 6 weeks until resolved to Grade 1 or less, stabilized, or returned to baseline, even after treatment discontinuation, if needed.	Hold study drug dosing until AE has resolved to ≤ Grade 1. Participants whose ocular symptoms and signs resolve to ≤ Grade 1 in ≤ 14 days may be allowed to resume study drug at the same dose level. Participants whose ocular symptoms and signs resolve to ≤ Grade 1 in > 14 and ≤ 28 days may resume study drug at 1 lower dose level with sponsor approval.
Grade 3	Complete eye examination. Participants should have weekly symptomatic ocular assessments and repeat eye examinations at least every 6 weeks until resolved to Grade 1 or less, stabilized, or returned to baseline, even after treatment discontinuation, if needed.	Hold study drug dosing. Participants whose ocular symptoms and signs resolve to ≤ Grade 1 in ≤ 28 days may resume study drug at 1 lower dose level with sponsor approval.

Grade (CTCAE v5.0)	Management	Guidelines for Dose Modification ^a
Grade 4	Complete eye examination. Participants should have weekly symptomatic ocular assessments and repeat eye examinations at least every 6 weeks until resolved to Grade 1 or less, stabilized, or returned to baseline, even after treatment discontinuation, if needed.	Permanently discontinue study drug.

Abbreviations: AE: adverse event; CTCAE: Common Terminology Criteria for Adverse Events.

Note: All participants are recommended to have an EOTV ophthalmic examination, regardless of whether they reported any ocular symptoms or signs. Participants with ongoing Grade 2 or greater ocular symptoms or signs must continue to have ophthalmic examinations at EOTV and during the follow-up period.

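### Protocol Section 7.2, Table 7 and Section 5.4 do not agree on when study drug may resume after an ocular event of Grade 2 or higher

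*Protocol*

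**What the plan says.** Four parts of the protocol bear directly on resuming treatment after an ocular event.

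- **Section 7.2 (Ocular Toxicity).** "If a participant develops ≥ Grade 2 ocular symptoms or signs, the study drug must be interrupted". The next sentence reads "Study drug may resume if ocular symptoms or signs improve to Grade 1 or baseline within 14 days (see Table 7 for details". No upper grade limit and no dose level are given.
- **Table 7 (Section 7.2.2).** For Grade 2, "Hold study drug dosing until AE has resolved to ≤ Grade 1". Resolution within 14 days allows the same dose level. For resolution after 14 and up to 28 days, the participant "may resume study drug at 1 lower dose level with sponsor approval". For Grade 3 resolving within 28 days, the same lower-level provision applies. Grade 4 means permanent discontinuation.
- **Section 5.4 (Guidelines for Study Drug Discontinuation).** The adverse events requiring discontinuation include a drug-related Grade 4 non-hematologic event and a DLT in the DLT period. Section 4.2.2 counts Grade 3 ocular symptoms and signs as DLTs.
- **Section 9.12 (Ophthalmic Examination).** For events above Grade 1, "treatment will be held until the participant is evaluated by an ophthalmologist for a complete examination (Section 7.2".

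Section 4.5.1 adds the general rule: "Dose delays of up to 21 days are allowed for participants who experience toxicity". It allows a restart after a longer delay with the sponsor's approval.

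**The concern.** Section 7.2 and Table 7 cover the same events with different conditions. Fourteen days is Table 7's cutoff for one case only, same-dose resumption after Grade 2. Section 7.2 applies it to every event from Grade 2 upwards. A site working from the text and a site working from the table could therefore treat the same participant differently.

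Ocular toxicity is a recognised risk of this payload class, and Section 7.2 says it has been seen in patients given this drug. The trial is planned for about 26 centers, so uniform handling depends on the written rule.

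The rule also shapes what is recorded. Discontinuations feed three things:

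- the expansion safety rule in Section 4.3, under which "enrollment will be paused within that cohort" when related events lead to discontinuation often enough;
- the SAP Section 7.2 tables of events leading to discontinuation;
- together with dose reductions, the eye-drop sub-study's example benchmark in Section 4.1.3.2, a "50% reduction in ocular AEs leading to dose reduction/discontinuation".

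**Working it through.** No sample size, power or error rate is involved, so the check is a comparison of passages.

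**Step 1. Section 7.2 against Table 7, by grade and day of resolution.**

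| Event | Section 7.2 as worded | Table 7 | Result |
|---|---|---|---|
| Grade 2, by day 14 | may resume, no dose stated | may resume, same level | agree |
| Grade 2, days 15 to 28 | condition not met | may resume one level lower, sponsor approval | differ |
| Grade 3, by day 14 | may resume, no dose stated | may resume one level lower, sponsor approval | differ on dose |
| Grade 3, days 15 to 28 | condition not met | may resume one level lower, sponsor approval | differ |
| Grade 2 or 3, after day 28 | condition not met | no provision to resume | agree |
| Grade 4, by day 14 | may resume | permanent discontinuation | differ |
| Grade 4, after day 14 | condition not met | permanent discontinuation | agree in effect |

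Four of the seven rows differ.

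**Step 2. The state that ends the hold.** Section 7.2 accepts a return to Grade 1 or to baseline. Table 7 requires Grade 1 or less. The two separate only when a participant's baseline finding is above Grade 1. Section 5.2 excludes corneal disorders and active ocular conditions needing treatment or monitoring, so this should be uncommon.

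**Step 3. Section 5.4 against the other two.**

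- Grade 4: Section 5.4 requires discontinuation for drug-related non-hematologic events. This matches Table 7 and contradicts the literal scope of Section 7.2.
- Grade 3 in the DLT period of dose escalation: the event is a DLT under Section 4.2.2, and Section 5.4 lists a DLT as requiring discontinuation. Table 7 lets the participant resume if the event resolves within 28 days, and makes no exception for the DLT period.

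**Step 4. Sections 4.5.1 and 9.12.** Section 4.5.1 allows up to 21 days, and longer with sponsor approval. Table 7 asks for sponsor approval for resolution after day 14 in Grade 2 and throughout in Grade 3, so its 28 days fit. Section 4.5.1 also refers to Section 7 for the resolution required. Section 9.12 sets no day limit and cites Section 7.2. Read alone, its hold would end at the examination and not at resolution, which is a looseness of wording.

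**Step 5. What moves downstream.**

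- A Grade 2 or 3 event resolving on days 15 to 28 could become a discontinuation at one site and a dose reduction at another. That can change the Section 4.3 count and the SAP discontinuation tables.
- The sub-study benchmark pools reduction with discontinuation, so that event counts either way. A Grade 3 event resolving by day 14 could move it, because Table 7 attaches a dose reduction and Section 7.2 names none.

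**The case against.** The strongest reply is that Section 7.2 is a summary. It permits resumption within 14 days without saying that this is the only route, it orders no discontinuation after day 14, and it sends the reader to Table 7. A careful site would follow the table. It is true that Section 7.2 does not itself stop treatment after day 14, so a reader who infers a mandatory stop goes beyond the text. A general footnote to the dose-modification tables does make discontinuation the default for insufficient recovery, unless toxicity-specific guidance says otherwise. Here that guidance is itself divided. The pointer also does not cure the mismatch: Section 7.2 sets a narrower condition than the table for some of the same cases and a wider one for Grade 4.

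Three stronger readings are tempting and are not supported.

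- **Section 9.12 as a third, looser rule.** It does not say that the examination alone releases the hold, and it cites Section 7.2. It is best read as an added examination requirement.
- **Section 4.5.1 as a competing 21-day limit.** Its provision for longer delays with sponsor approval makes it compatible with Table 7.
- **One event deciding whether a cohort pauses.** One of three participants does reach the threshold (1/3 = 33.3%, at least 33%), but that is a property of the pause rule for any related discontinuation and not a measure of this inconsistency.

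It can also be said that the SAP tables rest on the recorded action taken and so remain well defined, and that the sub-study benchmark is an example serving an exploratory objective. Both points stand. They limit the statistical consequence but do not remove the inconsistency in how participants are handled.

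**Conclusion.** The inconsistency is real and lies between Section 7.2, Table 7 and Section 5.4. It covers three situations: Grade 2 or 3 events resolving on days 15 to 28; the dose on resumption after a Grade 3 event resolving by day 14; and whether Grade 4 events, and Grade 3 events in the DLT period, may resume at all. The difference in the end-of-hold wording is minor.

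No stated statistical figure changes. The documents give no frequency for these events, so the number of participants affected is unknown. The consequence assumes that some sites will act on Section 7.2 without applying Table 7 in full, which the present wording permits. The point should be corrected because it concerns participant safety and the classification of a known toxicity.

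**What to change.** Section 7.2, Table 7, Section 5.4 and the wording of Section 9.12 must be reconciled. One controlling statement should give, by grade, the hold, the state that ends it, the time limit and the dose consequence. It should also say how that fits with the Section 5.4 entries for Grade 4 events and for DLTs. The other sections should refer to it without restating it, and the same end-of-hold wording should be used throughout. Section 9.12 should make clear how the examination relates to the resolution condition. Section 4.5.1 needs no change on this account. Which rule is right is a clinical decision on which no view is given here.

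The cost is wording in the next amendment, with no added procedures.
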